5.9. Unscheduled Visits/Lead Replacements

Subjects in Group 1 may require an unscheduled visit if they experience a technical issue with the stimulation system that the clinical staff has difficulty resolving over the phone, desire adjustments to stimulation parameters, require a bandage change or lead replacement, or experience an ADE which requires further evaluation by the clinical study staff. In the event of a device deficiency [REDACTED], site staff should contact SPR personnel to report the event.

It is possible that the leads may migrate from the intended target location or may become fully dislodged. In the event that a lead migrates or become dislodged, the Investigator may elect to place another lead. Throughout the 8-week PNS therapy for Group 1, the protocol allows for additional lead placements as necessary. This decision will be at the discretion of the Subject, Investigator and the Sponsor and should take into account the following considerations:

- 1) The subject's desire to continue with the therapy and understanding that the same risks of the initial lead placement would apply again,
- 2) The Investigator's belief that the intended target location is healthy enough to place another lead and there are no concerns with patient compliance with the care of the lead exit sites, and
- 3) The amount of time remaining in the home trial.

If the subject does not desire to continue with additional lead placements, they may continue with the schedule of follow-up visits per protocol (based on the date of Visit 4). Any additional lead placements in Group 1 will involve additional instances of Visit 4 (described above) and the associated requirements (e.g., subjects who initially required a pregnancy test prior to the first lead placement will have the test repeated as necessary). Subjects will then receive the remaining balance of the stimulation therapy. Subjects will have an additional exposure to the risks of lead placement, but the risks are the same as the risks detailed for the initial procedure.

5.10. Study Visit Windows

The acceptable windows for each visit are listed below in **Table 1**.

Table 1 Study Visit Windows

Visit Number	Visit Name	
1	Baseline	
2	Randomization	
3	Group 1: MBB Group 2: Diagnostic Procedure	
4	Lead Placement and Stimulation Programming (Group 1) / Standard Intervention (Group 2)	
5	1 week visit (Phone call for Group 2)	
6	2 week visit (Phone call for Group 2)	
7	3 week phone call	
8	4 week (1 month) visit	
9	5 week phone call	
10	6 week visit (Phone call for Group 2)	
11	7 week phone call	
12	8 week (2 month) visit (Lead Removal for Group 1)	
13	3 month follow up	
14	6 month follow up	
15	9 month follow up	
16	12 month follow up	
17	18 month follow up	
18	24 month follow up	
C1	Group 2: Crossover lead placement	
C2	Group 2: 4 week (1 month visit)	
C3	Group 2: 8 week (2 month visit) Lead Removal	
C4	Group 2: 3 month visit	
C5	Group 2: 6 month phone call	
C6	Group 2: 9 month phone call	
C7	Group 2: 12 month phone call	

5.11. Early Study Termination

It is possible that this study may be terminated prior to completing enrollment. As a result of the study design, the results will be reviewed and evaluated throughout the study as each subject completes his/her participation. If the results are less favorable than anticipated the study may be terminated early. Similarly, if it is found that the study yields results that are more favorable than expected, the study may be terminated earlier than expected. Any decision to terminate the study will be promptly reported to the IRBs and HRPO.

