	
primary endpoint will be assessed at 3 months after treatment with PNS or standard interventional management.
 
Average pain intensity will be measured for up to 24 months following treatment. Subjects will use numerical rating scales to record average pain intensity (BPI-5) and worst pain intensity (BPI-3) over the past 24 hours, and record daily analgesic medication usage each week at baseline, 1-, 2-, 3-, 6-, 9-, 12-, 18- and 24-months after treatment. The study will compare the efficacy of percutaneous PNS for the treatment of chronic low back pain to standard interventional management for the treatment of chronic low back pain, by evaluating if the treatment effect is equivalent (i.e., statistically non-inferior), and if so, if it is superior.
 
Sites (N)	Up to 30 sites
Subjects (N)	Up to 230 individuals will be randomized
Inclusion Criteria	
 • Age \geq 21 years and \leq 75 years • Able to understand and comply with study requirements and provide written informed consent • Chronic low back pain (i.e., pain lasting longer than 6 months, where the vast majority and center of pain is in the lumbar region, L1-L5 vertebral levels) • Reports an average low back pain score \geq 4 on a scale of 0-10 (BPI-5) • Previous use of at least two types of LBP therapies (e.g., medications, physical therapy, injections, etc.) • At least 4 weeks of stable pain treatment or medication as indicated by subject reported medication history (i.e., no new treatments or change in medication for pain in the last 4 weeks) • Reports active health insurance coverage (e.g., through commercial insurance, Medicare, Medicaid, Tricare)
Exclusion Criteria	
 • Radicular leg pain (e.g., pain that spreads to the lower extremities) or referred pain outside the lumbar region (e.g., sacral pain, hip pain) that is \geq 4 on a scale of 0-10, BPI-5 • Pain in the thoracic or cervical region that is \geq 4 on a scale of 0-10, BPI-5 • Pain from the sacroiliac joint, as determined by the Investigator • Signs of infection on or around the low back, or other conditions that increase risk to the subject in the opinion of the Investigator

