4.2.6. Sample Size & Justification

Up to 30 sites will participate in the study. The study will be planned with a maximum sample size of 230 enrolled subjects

Subjects will be randomized to either Group #1 or Group #2 using a 1:1 randomization scheme.

All subjects who sign a consent will receive a subject ID number. Subjects who sign a consent and do not meet all study eligibility criteria will be considered screen failures and not count against the number of enrolled subjects. Subjects who are randomized at Visit 2 will be counted as enrolled. If a subject does not receive the randomized intervention (e.g., complete PNS or receive a standard interventional procedure), their results may be excluded and/or analyzed separately from the rest of the population.

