7.3. Data Processing

All EDC study data and paper documentation will be monitored by SPR Therapeutics personnel (or their authorized representatives). Any missing or inconsistent data will be resolved via data queries.

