11.2. Criteria for Terminating the Study

SPR Therapeutics reserves the right to terminate the study at any time. SPR Therapeutics only intends to exercise this right for valid scientific or administrative reasons, and reasons related to the protection of Human Subjects participating in this study. Principal Investigators and IRBs will be notified in writing in the event of a study termination.

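### Section 5.11 permits ending the study early because results look good, with no link to a prespecified plan; depending on how the looks are done, the primary tests may exceed their nominal error rate

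*Protocol*

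**What the plan says.** Section 5.11 of the protocol makes three statements that belong together:

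- "It is possible that this study may be terminated prior to completing enrollment".
- "the results will be reviewed and evaluated throughout the study as each subject completes his/her participation". This is a commitment. The sentence opens by attributing the review to the study's design.
- "if it is found that the study yields results that are more favorable than expected, the study may be terminated earlier than expected". This is a permission. A matching sentence allows an early stop for disappointing results.

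The only procedure attached is prompt notice to the IRBs and HRPO. Section 5.11 names no threshold, reviewing body or plan, and refers to none.

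The sample size is a ceiling. Section 4.2.6 says "The study will be planned with a maximum sample size of 230 enrolled subjects", and the synopsis says "Up to 230 individuals will be randomized". Section 11.2 adds that "SPR Therapeutics reserves the right to terminate the study at any time", qualified by "SPR Therapeutics only intends to exercise this right for valid scientific or administrative reasons" and by reasons of subject protection.

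Section 4.3.1.1 sets the primary comparison: non-inferiority and then superiority of the proportion of subjects with at least a 50% reduction in average pain at 3 months.

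**The concern.** A final sample size that can depend on how good the results look is a sequential design. If each look compares the groups and the study may stop at a favourable one, a single fixed critical value no longer gives the stated error rate. The trials that do stop are also selected for a high observed difference.

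This is more than a detail left to the SAP. The protocol itself grants the permission. An SAP with a proper interim plan would still leave 5.11 allowing a favourable stop outside that plan. Section 11.2 does not close the gap, because good results could be called a scientific reason for stopping.

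At stake are both steps of the primary claim, and a reader's ability to tell whether an early significant result was tested at its nominal level.

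**Working it through.** **Nothing to reproduce.** The readable text gives no alpha, margin, response rates or accrual period, so the plan has no figure of its own to check. The question is how much error the permission could allow, and on what conditions.

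**Inputs from the protocol.** Maximum 230, allocated 1:1, so 230 / 2 = 115 per arm (4.2.6). Endpoint at 3 months (4.3.1.1). Participation ends at 24 months (5.7). Review as each subject completes (5.11).

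**Assumptions not in the protocol.** By-group review; critical value 1.96 (one-sided 0.025), unadjusted; even accrual over A years; Visit 4 on the day of randomization. Response rates under the superiority null are 30%, 40% or 50%. The non-inferiority null uses a margin of 10 points (30 v 40, 40 v 50) or 15 points (25 v 40, 35 v 50).

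**When looks occur on the literal reading.** The first 24-month completion is at t = 2 years. If A is 2 or less, enrollment is over by then and no look can cut it short. Otherwise, subjects per arm with 3-month data at time t number about 115 × (t − 0.25) / A:

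- First look (t = 2): 115 × 1.75 / A = 80.5, 67.1, 50.3, 40.3 for A = 2.5, 3, 4, 5.
- Upper limit for the last look (t just under A): 115 × (A − 0.25) / A = 103.5, 105.4, 107.8, 109.3.
- Randomized but not yet at 3 months, per arm: 115 × 0.25 / A = 11.5, 9.6, 7.2, 5.8.

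The simulated schedules tested 24 distinct per-arm sizes (80–103), 39 (67–105), 58 (50–107) and 69 (40–108).

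**Trigger 1: stop when z = (difference + margin) / SE reaches 1.96**, with margin 0 for superiority and SE unpooled (50,000 simulated trials). Ranges cover both tests.

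| Accrual | Randomized subjects included | Left out |
|---|---|---|
| 2 years or less | 0.023–0.030 (one analysis) | same |
| 2.5 years | 0.030–0.033 | 0.053–0.058 |
| 3 years | 0.035–0.039 | 0.064–0.069 |
| 4 years | 0.044–0.046 | 0.081–0.087 |
| 5 years | 0.048–0.052 | 0.091–0.100 |

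Looks earlier than the literal text would not need long accrual. Two unadjusted looks, at 58 and 115 per arm, give 0.041–0.046.

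**Trigger 2: stop on the observed difference**, same schedules, randomized subjects included, A = 2.5 to 5:

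- Superiority: 0.025–0.031 for a 10-point trigger, 0.030–0.045 for 15 points, 0.026–0.047 for 20 points.
- Non-inferiority (30 v 40, margin 10): about 0.025 to 0.03 for 15 or 20 points.

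The reason is visible in the difference needed for z = 1.96 at 40% response, 1.96 × √(2 × 0.4 × 0.6 / n). This is 12.7 points at n = 115, 15.2 at n = 80 and 21.5 at n = 40. A 10-point trigger stops many trials short of significance, so it adds few false positives.

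**Overstatement.** With trigger 1 and randomized subjects included, trials stopped for favourable results overstate a true 10-point difference (50% v 40%) by 7.0–9.4 points and a true 15-point difference (55% v 40%) by 4.0–6.0. Averaged over all trials the bias is smaller: +0.5 to +2.4 and +0.6 to +2.6 points.

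**The unfavourable stop alone** (observed difference 0 or below). False positives are 0.023–0.029, no higher than with one analysis. Power for 55% v 40% is Φ(0.15 / √((0.55 × 0.45 + 0.40 × 0.60) / 115) − 1.96) = Φ(2.30 − 1.96), about 0.64 without the stop and 0.61–0.64 with it.

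**The case against.** - **The review may be pooled, and a plan may exist.** Neither by-group review nor lack of adjustment is stated. Section 7.3 has sponsor personnel monitoring all study data, but for missing or inconsistent entries, so it shows access at most. By attributing the review to the design, 5.11 leaves room for a sequential design in redacted text or the SAP. This stands: a reader might infer that no rule exists anywhere, and the documents do not support that. What is established is that 5.11 grants the permission and cites no plan.
- **Participation lasts 24 months, so looks may come too late to matter.** This stands as a condition. The accrual period is not readable. Up to 30 sites for 230 subjects is compatible with either short or long accrual.
- **Doing better than expected is not the same as reaching significance.** This stands. The trigger is unstated, and some triggers cause no material inflation.
- **The figures of 0.05 to 0.10 need randomized subjects to be dropped after a stop.** No section says that. Section 8.0 says all primary and secondary outcome data will be analysed, and 8.1 commits to retention. The exclusion wording in 4.2.6 concerns subjects who do not receive their randomized intervention.
- **Looks and boundaries belong in the SAP.** True, and their absence is not the complaint. The complaint is a permission that stands whatever the SAP says.

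**Conclusion.** The point holds in conditional form. Section 5.11 permits a favourable stop on reviewed results with no link to a plan, while the sample size is only a maximum. If the review is by group, the stop is unadjusted and looks fall before enrollment ends, the primary tests may exceed their nominal rate and stopped trials overstate the difference.

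At an assumed one-sided 0.025 with 115 per arm, 2.5 to 5 years' accrual and randomized subjects included, the error is about 0.03–0.05 for a stop at significance. For a stop on a 10- to 20-point difference it is roughly 0.025–0.045 (0.047 in the highest case). It is not raised on the literal schedule if accrual takes two years or less.

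A reader might infer that the error rate is certainly inflated, or that it reaches 0.10. The documents support neither: the first depends on facts not shown, and the second on an exclusion that no section describes. The wording should be fixed; confidence that harm follows is medium.

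**What to change.** In 5.11, do one of the following:

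- (a) Delete the sentence allowing a stop on favourable results, and state that no by-group effectiveness results are used to stop or change enrollment before the last randomized subject's Visit 13.
- (b) State that a stop for effectiveness occurs only under the prespecified, alpha-controlled interim plan in the SAP, covering both primary tests, and cite it.

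Under either option, state that after any stop all randomized subjects are followed to Visit 13 and included in the primary analysis, and that any by-group looks already taken are reported. The stop for unfavourable results may stay if described as non-binding futility. Make 11.2 refer to 5.11 for stops based on effectiveness results.

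The cost is a few sentences in 5.11 and a cross-reference in 11.2. If the SAP already holds a plan, option (b) needs little more than the citation. The sponsor gives up ad hoc stopping for favourable results. New wording cannot undo looks already taken, which is why they should be reported.

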5.12. Subject Crossover

Subjects randomized to the control group (Group 2) may crossover to receive PNS after 12 months (Visit 16). The ability to crossover may depend on Investigator judgement related to the interventional procedure the subject received (e.g., if it conflicts with the SPRINT Instructions for Use).

Group 2 subjects who crossover to receive PNS and complete Visit C1 (lead placement) will then complete study visits to collect outcomes at 1-mo (Visit C2), 2-mo (C3), 3-mo (C4), 6-mo (C5), 9-mo (C6), and 12-mo (C7) after PNS lead placement. Visits C5 through C7 will be completed as phone calls. Outcomes at all crossover visits will be assessed in accordance with Appendix B. Women of childbearing age and reproductive potential will have a pregnancy test completed before or at Visit C1.

[REDACTED]

[REDACTED]

Subjects who are randomized to Group 1 (PNS), but wish to also receive RFA or another standard interventional management may elect to undergo any other treatments for low back pain at any point, however, the use of other therapies or interventions will be collected at study visits. Subjects electing to receive other treatments will still continue participation as Group 1 subjects (i.e., are not discharged from study, continue participation in study visit schedule as normal, and are not crossed over to Group 2 for the purposes of the study).

5.13. Subject Compensation

Individuals who are not 1) federal employees [civil servants] or 2) active military duty personnel will receive [REDACTED] compensation for taking part in all study visits. Compensation will be based on the subject completing milestones within the study. Federal Employees (civil servants) or active military duty

personnel who are not off duty or on leave during study visits would not be eligible for compensation. The disbursement schedule will be as follows:

- █ after the completion of Visit 1 – Consent
- █ after the completion of Visit 2 – Randomization
- █ after the completion of each Visit 3 – MBBs or Diagnostic Procedures
- █ after the completion of Visit 4 – Lead placement and stimulation programming (Group 1) or standard interventional management (Group 2)
- █ after the completion of each in-person early follow-up visit
- █ after the completion of each telephone call
- █ after the completion of each long-term follow-up visit

If a subject volunteers to participate in an additional Visit 4 (returns for another session of stimulation testing, lead replacement, or intervention), the subject will receive an additional █ compensation at the completion of that visit. All requirements for Visit 4 will be repeated. If a Group 2 subject crosses over to receive the PNS system, they will be compensated again for those visits:

- █ after the completion of Visit C1 – Lead placement
- █ after the completion of each Visit C2, C3, C4 in-clinic visits
- █ after the completion of each Visit C5, C6, C7 telephone calls

█ Subjects will also be compensated █ for unscheduled visits or follow-up visits related to ADEs.

6.0 INFORMED CONSENT PROCESS

In accordance with applicable regulations, it is the responsibility of the Principal Investigator to give each participant (or the participant's legally authorized representative) full and adequate verbal and written information about the objectives of the study, the study procedures, and the potential risks of participating in the study prior to inclusion in the study. Potential study participants will be informed that their participation is voluntary and that they may withdraw their consent at any time and for any reason without sanction, penalty, or loss of benefits to which they are otherwise entitled. Potential participants will also be informed that withdrawal from the study will not jeopardize their future medical care. It is the Principal Investigator's responsibility to obtain a signed Informed Consent Form from each potential study participant prior to performing any study-related procedures and to document the informed consent process in the subject record.

The Informed Consent Form will be amended whenever new information becomes available that may be relevant to the subjects continued participation. Modifications to the Consent Form must be approved by SPR Therapeutics prior to submission to the IRB. The investigator must also inform SPR Therapeutics of any IRB mandated revisions to the study protocol.

7.0 DATA COLLECTION AND MANAGEMENT

7.1. Data Collection

For this study, an Electronic Data Capture (EDC) system which utilizes electronic CRFs (eCRFs) will be used. A 21 CFR Part 11 compliant system will be selected for use which enables entry of study data into an Electronic Data Capture system by each participating clinical site or the subject directly.

Paper source documents, where applicable, will be completed and maintained in a fashion that is consistent with accepted Good Clinical Practices. If necessary, corrections to the source documentation will be made by using a single line strikeout with the initials and date of the person making the correction. The corrections will be made so as not to obscure the original data. Correction fluid or correction tape may not be used. All paper study documentation will be stored in a locked storage facility (either a locked office or a locked cabinet).

7.2. Confidentiality of Data

Every effort will be made to protect subject confidentiality. Subject names and personal identifiers will not appear in any publications resulting from this work. Subjects will be informed that the sponsor, the IRB, and regulatory authorities will have access to records that identify them as individuals. All applicable HIPAA regulations will be followed.

7.3. Data Processing

All EDC study data and paper documentation will be monitored by SPR Therapeutics personnel (or their authorized representatives). Any missing or inconsistent data will be resolved via data queries.

7.4. Subject Screening and Identification Log

A subject screening log will be completed at the clinical site for all subjects who were considered for the study. Those individuals who are excluded will be listed along with the reason for exclusion. Any subject who signs an Informed Consent and does not proceed with procedures associated with treatment or fails to meet eligibility (e.g., baseline diary back pain score < 4) will be considered a screen failure. The Subject Identification log will be completed for subjects enrolled in the study.

7.5. Subject Numbering

Screened and consented consecutive subjects will be given a unique Subject ID number. Subjects who sign consent and do not meet all study eligibility criteria will be considered screen failures and not count against the number of enrolled subjects. Subjects who are randomized at Visit 2 will be counted as enrolled. A number will be assigned consecutively to each subject at each clinical site. A master list linking the subjects to the unique "Subject ID" numbers will be kept by the study staff in a secure location.

8.0 DATA ANALYSIS AND STATISTICAL METHODS

All primary and secondary outcome data will be analyzed and reported. Each clinical site or individual clinician may be analyzed separately. The study objective is to compare the safety and effectiveness of percutaneous PNS for the treatment of low back pain to standard interventional management. The study will determine if the treatment effect of percutaneous PNS is equivalent (i.e., statistically non-inferior), and if so, if it is superior, to standard treatment with standard interventional management.

8.1. Plan to maximize subject retention and minimize loss of data

Significant efforts will be made to maintain maximum subject retention and follow up data and minimize the percentage of missing data.

Prior experience indicates a potential cause of data loss is when a lead is dislodged or removed before scheduled end of PNS therapy (60 days).

Additional instructions have been provided regarding bandaging to the subjects to minimize the chance of accidental lead dislodgement.

Subject withdrawal from the study is a potential source of data loss. Study investigators and staff will be trained to have clear discussions with subjects considering withdrawing from the study. During the discussions, subjects will be reminded that they may withdraw from the study at any time and investigators will determine if any burdens of continuing in the study can be eased to enable participation at a level that is more amenable to the subject. For example, if subjects indicate a lack of interest in continued participation, they can be offered an opportunity to provide only the most essential and easily collectable data (e.g., recall pain scores and AE questions regarding their safety). To further reduce burden associated with time and travel to the clinical site, subjects can be provided with the option to complete AE questions, surveys, or diaries over the phone or return these via other methods (e.g., a preaddressed, postage-paid envelope, email, ePro, etc).

Subjects in either group may continue to participate in the study visits independent of their successful completion of diagnostic procedures and/or standard interventional management. These subjects may be offered the option to continue with the study and provide only the most essential and easily collectable data (including the option of switching to all telephone calls and completing the most important visits). Subjects also have the option to receive SOC LBP treatments from their regular, outside medical providers (i.e., not exclusively from the study site). If so, these subjects will continue to be followed by the site for research only visits/calls. Alternative options may be utilized to minimize data loss in subjects.

Subjects may elect not to undergo a diagnostic procedure and/or treatment (e.g., subject elects to continue their usual care for back pain) but are still willing to remain in the study. In this event, if the subject has not undergone a diagnostic procedure by the end of the Visit 3 window, they will progress directly to Visit 4 (i.e., Visit 3 will be marked as "missed" and Visit 4 will be completed via phone). Regardless of the mode of participation, subjects

who continue participation through 12 months after "Start of Treatment" (completion of Visit 16) will be eligible for crossover.

Subjects are offered compensation for each visit as it is completed, including unscheduled visits, even if they do not complete all the visits. This compensation is intended to cover costs associated with taking the time to participate in the study. [REDACTED]

A potential source of data loss is the failure of the subjects to return their completed diaries. Thus, subjects may receive reminder calls from the clinical study staff before certain visits to remind them to bring their completed diaries with them to the visit. For long-term follow up visits, subjects may complete a diary after a visit and return via mail/email if the original diary for that visit was lost or was not completed. Diaries may also be completed electronically.

If a subject is unable to return any follow-up diary, the data may be replaced using the one-week recall data (question #3 or #5 of the validated BPI-SF). If the subject later returns the diary, the diary data will be used over the one-week recall data. If a subject is unable to return to the clinic for a visit, options to collect the most important assessments (e.g., pain intensity, ODI) and data (e.g., LBP treatment use, adverse events, etc.) will be made available to the subject (e.g., assessment of surveys and visit questions via phone or video call, remote completion of surveys via mail, email, ePro, etc.). These options will mitigate the problem of missing data and minimize the need to impute scores. Scores will only be imputed if recall (or remotely collected) data are unavailable and cannot be obtained.

Additional steps will be taken as necessary to maintain a high level of subject participation and follow up. For example, if a subject relocates during the study, arrangements will be made either to provide transportation for the subject to attend their visits at the clinical site, or to allow the subject to receive the necessary follow up at a medical center in closer proximity to their new location and a referring physician located near the subject will conduct the visit with the assistance of an investigator and/or a technical representative from SPR Therapeutics as needed. In the event of a local or national emergency (e.g., pandemic, natural disaster, safety concern), visits may be performed by phone if necessary. These rare instances should be reviewed and approved by the Sponsor prior to completion.

